9.2.2 Reporting Procedures for Serious Adverse Events

The investigator is responsible for ensuring that all serious adverse events observed by the investigator or reported by the subject that occur after signing of the informed consent through 30 days after the last dose of investigational product or the EOS visit (whichever is later) are recorded in the subject’s medical record and are submitted to Amgen. All serious adverse events must be submitted to Amgen within 24 hours following the investigator’s knowledge of the event via the applicable eCRF.

After the protocol-required reporting period defined above, the investigator does not need to actively monitor subjects for serious adverse events. However, if the investigator becomes aware of a serious adverse event after this protocol-required reporting period, the investigator will report the event to Amgen within 24 hours of the

investigator's knowledge of the event. Serious adverse events reported outside of the protocol-required reporting period will be captured within the safety database as clinical trial cases for the purposes of expedited reporting.

The serious adverse event must be submitted to Amgen within 24 hours following the investigator's knowledge of the event via the applicable CRF. If the electronic data capture (EDC) system is unavailable to the site staff to report the serious adverse event, the information is to be reported to Amgen via an electronic Serious Adverse Event (eSAE) Contingency Report Form within 24 hours of the investigator's knowledge of the event. See [Appendix B](#) for a sample of the eSAE Contingency Reporting Form. For EDC studies where the first notification of a Serious Adverse Event is reported to Amgen via the eSAE Contingency Report Form, the data must be entered into the EDC system when the system is again available.

The investigator must assess whether the serious adverse event is possibly related to the investigational product. This relationship is indicated by a "yes" or "no" response to the question: Is there a reasonable possibility that the event may have been caused by the investigational product?

The investigator must assess whether the serious adverse event is possibly related to any study mandated activity or procedure. This relationship is indicated by a "yes" or "no" response to the question: Is there a reasonable possibility that the event may have been caused by a study activity/procedure?

The investigator is expected to follow reported serious adverse events until stabilization or reversibility.

New information relating to a previously reported serious adverse event must be submitted to Amgen. All new information for serious adverse events must be sent to Amgen within 24 hours following knowledge of the new information. The investigator may be asked to provide additional follow up information, which may include a discharge summary or extracts from the medical record. Information provided about the serious adverse event must be consistent with that recorded on the applicable eCRF (eg, Adverse Event Summary eCRF).

If a subject is permanently withdrawn from protocol-required therapies because of a serious adverse event, this information must be submitted to Amgen.

Amgen will report serious adverse events and/or suspected unexpected serious adverse reactions as required to regulatory authorities, investigators/institutions, and IRBs/IECs

in compliance with all reporting requirements according to local regulations and good clinical practice (GCP).

The investigator is to notify the appropriate IRB/IEC of serious adverse events occurring at the site and other adverse event reports received from Amgen, in accordance with local procedures and statutes.

9.3 Pregnancy and Lactation Reporting

If a pregnancy occurs in a female subject, or female partner of a male subject, while the subject is taking protocol-required therapies report the pregnancy to Amgen as specified below.

In addition to reporting any pregnancies occurring during the study, investigators should monitor for pregnancies that occur through 30 days after the last dose of protocol-required therapies.

The pregnancy should be reported to Amgen Global Patient Safety within 24 hours of the investigator's knowledge of the event of a pregnancy. Report a pregnancy on the Pregnancy Notification Worksheet ([Appendix C](#)).

If a lactation case occurs while the female subject is taking protocol-required therapies report the lactation case to Amgen as specified below.

In addition to reporting a lactation case during the study, investigators should monitor for lactation cases that occur through 30 days after the last dose of protocol-required therapies.

Any lactation case should be reported to **Amgen Global Patient Safety** within 24 hours of the Investigator's knowledge of event. Report a lactation case on the Lactation Notification Worksheet ([Appendix C](#)).

10. STATISTICAL CONSIDERATIONS

10.1 Study Endpoints, Analysis Sets, and Covariates

10.1.1 Study Endpoints

Primary Endpoints:

- Safety: subject incidence of TEAEs, DLTs, and clinically significant changes in vital signs, ECGs, physical examination findings, and clinical laboratory tests

Secondary Endpoints:

- PK of AMG 211 after continuous intravenous (cIV) infusion across 2 cycles
- Incidence of anti-AMG 211 antibody formation
- Time to progression (TTP)

- 6-month progression-free rate
- Efficacy parameters: overall response rate (ORR; per modified irRC), duration of response, time to response

Exploratory Endpoints:

- Changes in methylation and mutations in circulating free DNA present in plasma
- Lymphocyte counts, T-cell activation and immune checkpoint regulator status
- Changes in serum cytokine levels
- Biomarkers and mutations in tumor cells
- Changes in circulating tumor cells (CTCs)
- Soluble CEA serum levels

10.1.2 Analysis Sets

The analysis of all endpoints, unless noted otherwise, will be conducted on the Safety Analysis Set defined as all subjects that are enrolled and receive at least 1 dose of AMG 211.

The analysis of DLT will be restricted to DLT-evaluable subjects. The DLT window is 28 days for all cohorts and is independent of the length of the infusion. A subject is not DLT-evaluable if he/she drops out before completion of cycle 1 for reasons other than an adverse event related to the investigational product. Ineligible subjects may be replaced.

The PK Analysis Set will contain all subjects who have received at least 1 dose of the investigational product and have at least 1 PK sample collected. These subjects will be evaluated for PK analysis unless the number of data points required for analysis is not enough, or significant protocol deviations have affected the data, or if key dosing or sampling information is missing.

10.1.3 Covariates and Subgroups

The relationship of the following covariates to efficacy endpoints will be explored if appropriate.

- Changes in methylation and mutations in circulating free DNA present in plasma
- Lymphocyte counts, T-cell activation, and immune checkpoint regulator status
- Serum cytokine levels
- Biomarkers and mutations in tumor cells
- Change in CTCs
- sCEA levels

10.2 Sample Size Considerations

It is anticipated that approximately 78 subjects will be enrolled in this study.

Approximately 39 subjects will be enrolled in the dose-escalation cohorts and approximately 39 subjects will be enrolled in the dose-expansion cohorts.

The sample size in dose-escalation cohort is determined empirically and is consistent with this type of study using a modified TPI Bayesian model design (Bailey et al, 2009; Neuenschwander et al, 2008).

Refer to [Appendix E](#) for details of the modified TPI Bayesian model, the average sample size, and other design operating characteristics.

In the dose-escalation cohorts, with 3 DLT-evaluable subjects per dose level, there is a 49% to 73% probability of observing at least 1 DLT if the true DLT rate is 20% to 35%.

In the dose-expansion cohorts, with 39 subjects there is a 86% probability of observing at least one adverse event with 5% incidence rate. In the dose-expansion cohorts, an exact 80% binomial confidence interval (CI) will be provided for the ORR. With 39 subjects and 20.5% ORR, the expected 80% CI and its half-width would be 12.3% to 31.2% and 9.5%, respectively.

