10.4.3.3 Efficacy Parameter Analysis

Listings will be produced for all subjects in the dose-escalation cohorts and the dose-expansion cohorts indicating the time to progression, objective response, time to response, and duration of response. The proportion of subjects with an ORR with corresponding exact 80% CI will be calculated using the Clopper-Pearson method ([Clopper and Pearson, 1934](#)) and tabulated for subjects treated at the MTD. The proportion of subjects that are progression free at 6 months with corresponding exact 80% CI will be calculated using the Clopper-Pearson method. Kaplan Meier curve will be presented for time to tumor progression with estimates for rates and 80% CI at selected weeks.

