10.6.2 Best Overall Response

The number and percentage of subjects with a best overall disease/tumor response of complete response (irCR), partial response (irPR), stable disease (irSD) or progressive disease (irPD) will be presented for the dose escalation and/or expansion parts of the study. Subjects with best overall response of irSD should meet a minimum duration of 8 weeks at the time of scan.

In addition, the proportion of subjects treated at MTD with an overall response (ORR) and corresponding exact 80% confidence interval calculated using the Clopper-Pearson method ([Clopper and Pearson, 1934](#)) will be tabulated. Unevaluable subjects treated at MTD will be treated as non-responders and included in the calculation of ORR.

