10.6.3 Time to Progression

Kaplan Meier curve will be presented for time to tumor progression with estimates for rates and 80% CI at selected weeks. Subjects treated at MTD will be included for this analysis.

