10.6.5 Tumor Burden

At each on-study radiological assessment, tumor burden will be derived as the sum of the products of the longest perpendicular diameters of the all index and new measurable lesions will be recorded. Baseline tumor burden will be the sum of the products of the 2 longest perpendicular diameters (SPD) of all the index lesions. The percentage change from baseline in tumor burden and percentage change from nadir will be recorded on the eCRF:

Individual subject time profiles of the percentage change from baseline will be generated for each part of the study. The initial dose group and primary tumor type will be highlighted.

For the dose escalation, the maximum percentage improvement (maximum decrease or minimum increase over the whole study) in the tumor burden will be plotted for each subject (waterfall plot). The initial dose group, primary tumor type and best overall response will be highlighted. This analysis will be repeated for subjects in the dose expansion part of the study.

In addition, summary statistics on percentage change from baseline by time point will be generated for subject treated at MTD.

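### The ORR precision in Protocol 10.2 is for all 39 expansion subjects, but the planned CI is for subjects at the MTD, and SAP 7.1 cannot group a multi-dose expansion by dose

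*Protocol*

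**What the plan says.** **Stated precision.** Protocol 10.2 makes the commitment for the expansion as a whole: "In the dose-expansion cohorts, an exact 80% binomial confidence interval (CI) will be provided for the ORR". It then gives the expected result: "With 39 subjects and 20.5% ORR, the expected 80% CI and its half-width would be 12.3% to 31.2% and 9.5%, respectively". The same paragraph gives an 86% chance of seeing at least one adverse event of 5% incidence among 39 subjects.

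**Planned analysis.** Protocol 10.4.3.3 has the ORR and its exact 80% interval "tabulated for subjects treated at the MTD". SAP 10.6.2 agrees, planning "the proportion of subjects treated at MTD with an overall response (ORR) and corresponding exact 80% confidence interval". It adds that unevaluable subjects at the MTD count as non-responders. Before that, SAP 10.6.2 plans best-overall-response counts for escalation and/or expansion, without an interval.

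**Who is in the expansion.** Protocol 3.1 plans about 39 subjects at multiple dose levels. About 29 also take part in the Imaging Study and may be at the MTD, the recommended phase 2 dose (RP2D) or a lower dose. The others, about 10, receive the MTD or RP2D. No split by dose is given. Table 3 also allows the highest tested dose if no MTD is reached. Protocol 6.2.1.1 mentions only the MTD or RP2D for the expansion.

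**Grouping rule.** SAP 7.1 analyses escalation subjects by initial dose received, but expansion subjects by the one dose selected for that part. The SAP is written to the protocol of 24 March 2014 and describes an expansion of up to 10 (SAP 1, 3.1.2, 3.2). Protocol 10.4.2.1.1 requires adverse events overall and by dose level.

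**Related endpoints.** Protocol 10.4.3.3 plans "The proportion of subjects that are progression free at 6 months with corresponding exact 80% CI" with no MTD restriction, and Protocol 10.1.2 sets the default: "The analysis of all endpoints, unless noted otherwise, will be conducted on the Safety Analysis Set". SAP 10.6.3 and 10.6.4 restrict time to progression and the 6-month rate to the MTD: "Subjects treated at MTD will be included for this analysis". SAP 10.6.5 does the same for one summary: "summary statistics on percentage change from baseline by time point will be generated for subject treated at MTD".

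**The concern.** A precision statement should describe the estimate that will be reported. Here the stated interval belongs to all expansion subjects, and the tabulated interval belongs to one dose. The two groups differ in both directions. The expansion may contain many subjects who are not at the MTD, and subjects treated at the MTD may include some from escalation. Someone reading 10.2 would expect a half-width of about 9.4 points in the ORR table, and the MTD table could be about twice as wide.

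The SAP 7.1 problem reaches the primary endpoint, because adverse-event incidence is summarised by dose. Applied literally to a multi-dose expansion, the rule either places lower-dose subjects in the selected-dose column or finds no single dose to apply.

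**Working it through.** **Inputs.** From Protocol 10.2: n = 39, ORR 20.5% (8/39), exact two-sided 80% interval. From Protocol 3.1: about 29 Imaging Study subjects, leaving 39 − 29 = 10. From Table 3: 3 to 6 subjects per escalation cohort.

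**Formula.** Clopper-Pearson with x responders among n: lower limit = Beta(0.10; x, n − x + 1), upper limit = Beta(0.90; x + 1, n − x), where Beta(q; ·) is the q-quantile. Half-width = (upper − lower)/2.

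**The plan's own figures.** 8/39 gives 12.33% to 31.18%, so the half-width is (31.18 − 12.33)/2 = 9.42 points. The printed 9.5 follows from the rounded limits: (31.2 − 12.3)/2 = 9.45. For adverse events, 1 − 0.95^39 = 0.865, in line with the stated 86%. Both figures are right for 39 pooled subjects.

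**Precision by size of the MTD group.** The documents give no split, so the sizes below are assumptions. They take the RP2D to equal the MTD and use whole numbers of responders near 20%.

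| Assumed MTD group | n | x/n | Exact 80% CI | Half-width (points) | Ratio to 9.42 |
|---|---|---|---|---|---|
| All 29 imaging subjects lower, no escalation subjects counted | 10 | 2/10 | 5.4% to 45.0% | 19.8 | 2.1 |
| As above, plus 3 from escalation | 10 + 3 = 13 | 3/13 | 8.8% to 44.4% | 17.8 | 1.9 |
| Same n, one responder fewer | 13 | 2/13 | 4.2% to 36.0% | 15.9 | 1.7 |
| As the first row, plus 6 from escalation | 10 + 6 = 16 | 3/16 | 7.1% to 37.1% | 15.0 | 1.6 |
| All expansion subjects at the MTD | 39 | 8/39 | 12.3% to 31.2% | 9.4 | 1.0 |
| All expansion subjects at the MTD, plus 6 from escalation | 39 + 6 = 45 | 9/45 | 12.4% to 29.7% | 8.6 | 0.9 |

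The n = 10 row agrees with SAP 3.2, which gives 5.4% to 45.0% and 19.8% for its original expansion of 10.

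**Grouping rule.** With one expansion dose, the SAP 7.1 rule gives the right table. With two or more doses, the dose selected for this part is either one of them, so subjects at other doses are misgrouped, or it is undefined. Neither outcome gives the by-dose adverse-event table in Protocol 10.4.2.1.1.

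**The case against.** **The two ORR statements can coexist.** Protocol 10.2 may describe a pooled expansion interval reported alongside the MTD table, since SAP 10.6.2 already plans expansion response counts. This stands in part: the passages do not exclude a pooled interval. But no analysis section attaches one to the pooled group.

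**The wide interval is a corner case.** The largest ratio needs all 29 imaging subjects at a lower dose and no escalation subjects counted. That is correct, and the range also runs slightly below 1.

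**SAP 7.1 reflects an older protocol.** It works for the design it was written for, so a reader should not infer that the SAP never had a usable rule. The initial dose group is also highlighted in the SAP 10.6.5 profiles and waterfall plots. The rule still fails for the current expansion.

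**The time-to-progression mismatch.** A reader might call this a contradiction. Protocol 10.1.2 lets a different population be noted, and the SAP notes one, so it is mainly a refinement.

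**The MTD if no DLT occurs.** A reader might infer that the model rule would then name 6400 µg/day. The documents do not support that, because the answer depends on d_max, defined in Appendix E as the maximum planned dose, and the amended plan reaches 12800. Using the Appendix E prior and no DLTs at 200 to 6400:
- With d_max 6400 and 3 subjects per level, 6400 has target probability 0.17 and overdose probability 0.07, and the rule names it.
- With d_max 12800 and 6 per level, 12800 has 0.20 and 0.22, and the rule names 12800.
- With d_max 12800 and 3 per level, 12800 is barred, at 0.27 against the 0.25 limit.

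Only the general point stands: the rule can name a dose with no DLT, while Table 3 speaks of not reaching an MTD.

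**Conclusion.** The concern holds as a mismatch of populations. The calculation in 10.2 is correct, but it matches the planned MTD table only if about 39 subjects are treated at the MTD. Over assumed MTD groups of 10 to 45, the half-width is about 19.8 to 8.6 points, or 2.1 to 0.9 times the value for 8/39. This rests on an ORR near 20% and an RP2D equal to the MTD. The group could be smaller if the two doses differ, or larger if cohorts or schedules are pooled.

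SAP 7.1 needs correcting for the amended expansion because it affects by-dose safety summaries.

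The consequence is moderate: ORR is secondary and no decision rule uses the interval width. Nor is the analyst left free to pick the ORR population in general. Where an MTD is declared, Protocol 10.4.3.3 and SAP 10.6.2 agree on subjects at that dose, and the SAP fixes how unevaluable subjects count. The open matters are the pooled interval, the escalation subjects, the schedules and the case of no declared MTD.

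**What to change.** 1. **Protocol 10.2.** Label the n = 39 ORR and adverse-event figures as pooled across expansion doses. Add ORR precision for the MTD/RP2D dose group at sizes marked as assumptions, for example n = 10, 13, 16, 39 and 45.
2. **Protocol 10.4.3.3 and SAP 10.6.2.** State whether the interval is given for the pooled expansion, the MTD group or both; whether escalation subjects at that dose count; and whether 14-day and 28-day schedules are pooled or shown separately. State that if no MTD is declared, the group is the dose taken into expansion under Protocol 10.3.1.
3. **SAP 7.1, 3.1.2 and 3.2.** Analyse expansion subjects by initial dose received, as for escalation, and update the description and size of the expansion.
4. **Minor alignment.** Use the same population wording for time to progression and the 6-month rate in Protocol 10.4.3.3 and SAP 10.6.3 and 10.6.4.
5. **Reconciliation by the sponsor.** Protocol 3.1 and 6.2.1.1 differ on whether lower doses are used in the expansion, which determines who is in the MTD group. No dose is proposed here.

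The cost is text and table-shell edits, with no change to enrolment or data collection. The stated precision becomes a range and may look less favourable.

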10.3 Planned Analyses

The following data analyses are planned: (1) dose decision analyses in the dose-escalation cohorts after every 3 to 6 DLT-evaluable subjects, (2) a safety review of dose escalation after all subjects in dose escalation have had the opportunity to complete 6 months of treatment, (3) the primary analysis after all dose-escalation and dose-expansion subjects have completed 6 months of treatment, and (4) the final analysis after all subjects have ended the study.

10.3.1 Interim Analyses

The DLRT (see [Section 10.3.2](#)) is responsible for all dose level decisions during dose escalation. Dose decisions are planned after every 3 to 6 subjects are enrolled throughout the dose-escalation cohorts. The DLRT considers the recommendation for subsequent doses based on the following rules:

- Based on the modified TPI Bayesian model, the next dose is the one with the highest probability of the target TPI (0.20, 0.35), but with a less than 0.25 probability of an excessive or unacceptable TPI.
- If ≥ 1 subject has a DLT at a dose level, then dose escalation cannot occur unless there are 6 or more DLT-evaluable subjects at that dose level. However, if a transient cytokine-release syndrome is reported as the DLT, but resolves within

48 hours and can be managed with prophylactic corticosteroids, the DLRT may decide to escalate the dose with the institution of prophylactic corticosteroid administration.

- The maximum allowed dose increase will be 1 dose level above the maximum of previous evaluated doses.
- Dose escalation can be achieved by evaluating a higher dose level with the same infusion duration (eg, 800 µg/day for 14 days to 1600 µg/day for 14 days), or by evaluating the same dose level with a prolonged infusion duration (eg, from 800 µg/day for 14 days to 800 µg/day for 28 days). The DLRT may also decide to explore in parallel both options mentioned above after the dose-escalation decision is made, or to prioritize one schedule. In this case, 2 TPI models may be run in parallel to obtain dose recommendations for these 2 schedules separately.
- Intermediate dose levels not pre-specified may be considered based on the optimal dose recommended by the TPI model.

The DLRT is responsible for making the decision to end dose escalation. Generally, the DLRT may consider the dose escalation complete if 1 of the following rules is met:

- The highest planned dose level is evaluated and no DLTs occur at any dose level. In this case the maximum administered dose will be used in a dose-expansion cohort.
- The TPI Bayesian model recommends the same dose 3 times (not necessarily sequentially).
- A total of approximately 39 DLT-evaluable subjects have been enrolled.

The Amgen Medical Monitor and Amgen Global Safety Officer can make dose decisions without convening the DRLT in the following limited circumstances:

- If a cohort has at least 3 DLT-evaluable subjects and 1 subject experiences a DLT, then the Amgen Medical Monitor and Amgen Global Safety Officer may decide to expand the number of subjects treated in this cohort.
- The Amgen Medical Monitor (or EDL) and Amgen Global Safety Officer may decide to open the next cohort using a de-escalated dose (de-escalated from the dose level of the most recent cohort), if this de-escalated dose had been previously evaluated by the DLRT.

A safety review of dose escalation is planned after all subjects in dose escalation have had the opportunity to complete 6 months of the treatment.

